We estimate in this pilot study that 12 children will be referred for investigations (based on referral of 2% children with the poorest growth) and that 30-40% of these investigated in clinic will have an underlying medical disorder identified (n=4-5) based on the published literature. This pilot study is not designed to evaluate whether the age at diagnosis is significantly reduced using an automated screening approach; rather, our pilot data will inform feasibility and acceptability for a larger NIHR grant application to test the screening programme at scale with a primary outcome of age at diagnosis of medical disorders.
We will also investigate the inter-test agreement between the heights measured by caregivers using a smartphone app and heights measured by health professionals using a stadiometer.
Aim 2
Aim 2 of the pilot study will generate pilot data to investigate the best indicators to detect poor school readiness and/or developmental problems in early childhood.
We will investigate whether the addition of growth and development data to other environmental and socioeconomic variables increases the pick-up rate of children at risk of poor school readiness and/or children with delayed development.
Growth will be assessed using three height measurements as described above and development assessed as part of standard care by a Health Visitor and practice nurse.
As part of routine care, each child's development will be assessed using both the caregiver and health visitor components of the ASQ-3. Following the 2.0-2.5 year contact, a random sample of 150 children will also be invited to enrol in a sub-study to generate pilot data to investigate the correlation between the ASQ-3 and development assessed by a child psychologist using a

	Gold Standard development battery, the Griffiths Mental Development Scale (GMDS). The GMDS will be used to measure gross motor, fine motor, social, language, visual-spatial and practical reasoning skills. These data will inform a larger NIHR grant application to test the sensitivity of the parental and health visitor components of the ASQ-3.
	We will use the data to conduct analyses to test the hypothesis that linear growth failure either alone or in combination with additional factors identifies children with reduced neurodevelopment, who are therefore at risk of poor school attainment.
Study duration	3 years

5. Introduction

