Using this approach, we are maximising opportunities to measure child growth at preschool ages by using existing contact points with health visitors and GP surgeries, and providing parents with the opportunity to measure their child's height using a novel smartphone app. Longitudinal height measurements, together with data collected on parental height, will be offered up to an automated growth-screening algorithm that we have developed using existing national datasets. Children with the most severe growth faltering (bottom 2-3% of children) will be identified and their caregivers/parents contacted to offer them referral to the paediatric endocrinology service at the Royal London Hospital for investigation of medical disorders of growth ([name]).

9. Study procedures

Children will be identified from the central health visitor lists held by the Health Visiting team at the Tower Hamlets GP Care Group (GPCG), which is a federation of 36 General Practices in Tower Hamlets and a partner in Tower Hamlets Together, a local integrated care partnership. From these lists, children will be randomly selected, with replacement, in two groups: i) the main growth study (N=480), and ii) the growth and development sub-study (N=150), for a total of 630 children. Group 1 will only undergo growth screening, and group 2 will additionally have a gold standard child development assessment conducted at baseline.

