
leads the paediatric endocrinology clinic to which the children will be referred, and will enter any relevant clinical data onto the REDCap database.

Sub-studies

Development sub-study

A randomly selected subset of 150 children will also be invited to an additional appointment with a child psychologist for a detailed developmental assessment, which is not part of standard care; children in this sub-study will be enrolled using a separate consent form (Form 5). The caregiver will be asked to provide written informed consent and to keep a copy of the PIS. The primary caregiver must have parental responsibility to provide consent. Assent will not be sought since all children will be between 3 and 4 years old.

Where the developmental assessment suggests the child may be experiencing developmental delay, the study psychologist may share the Griffith's report with the child's Health Visitor with the parent's permission. Reports will not be generated for all children and will only be generated when concerns are identified. The Griffith's assessment result is not a formal diagnosis but can provide extra context for a clinician.

Qualitative sub-study

Following the first contact, we will invite a subgroup of participants in the study (caregivers) and health visitors working in Tower Hamlets to take part in focus groups. A total of 16 caregivers will be selected from the sample of children participating in the study to participate in two focus groups of between 6 and 8 participants. Caregivers participating in focus groups will be consented using a separate PIS (PIS 16) and consent form (Form 14).

We will also conduct one focus group with health visitors. A total of eight health visitors currently working within the Healthy Child Programme in Tower Hamlets will be sampled with the help of the health visiting team at the Tower Hamlets GPCG. Separate PIS and consent forms will be used for health visitors (PIS 17, Form 14).

Clinical sub-study secondary analysis

A separate clinical sample of children with diagnosed growth disorders will be analysed to test the algorithm and obtain optimal cut offs for growth screening. In order to obtain a height measurement previous to the child's first attending growth clinic, we will seek to link the children's clinical data to their NCMP height measurement (measured at school and recorded by NHS England at 4 or 5 years old).

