At each of the 3 measurements of height we will identify the 2-3% of children with the poorest growth, as categorised by the algorithm (based on parental height, child height, and child growth velocity), in whom prior studies show a high prevalence (30-40%) of medical disorders. We will contact parents of these children to offer referral to the paediatric endocrinology clinic at the Royal London Hospital. A member of the study team will call the parents to inform them and will write to the child's GP to request a referral into the Royal London Hospital clinic via the e-referral system. We will evaluate acceptability and feasibility of the screening and referral process, using parental and primary care staff questionnaires. We will evaluate uptake by calculating the proportions screened, referred, investigated in clinic and diagnosed with medical disorders. At the clinic, children will be assessed by a paediatric endocrinologist and will undergo routine medical evaluation for short stature, with appropriate follow-up.

Development sub-study (age 2.0-2.5 years):

A random sample of 150 children will also be invited to enrol in a sub-study to generate pilot data on the sensitivity of the parent-reported ASQ-3 to assess child development compared to a gold standard development battery, the GMDS, undertaken by a psychologist. These children will undergo a neurodevelopmental assessment during their routine health visitor visit of their motor, cognitive, language and social skills using a standardized test battery (GMDS) by a child psychologist. Using data from the ASQ-3 developmental assessments conducted at baseline and follow up visits by the health visitor, we will investigate relationships between growth and development and assess content validity of the ASQ-3 by comparing it with the GMDS.

[figure not shown]
Qualitative sub-study (following the 2-2.5 year visit)

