growth being referred to clinic for further investigation. The proportion of children with complete observations, including height at three time points and parental height, will be compared to the proportion of children with fewer observation points or missing parental height. Descriptive statistics will be reported: the number and percentage of children found to be stunted and their characteristics (height, gender, age, socio-demographic factors). We will also report the number of children referred to clinic, attending clinic and found to have underlying medical conditions. The age at which each condition is identified will be reported and compared to the average age at diagnosis.

Height data collected by parents using a smartphone app will be analysed. The number of parents consenting to use of the smartphone app and reporting one or more height measurements through the app will be reported. The number of time points at which parent's upload smartphone measured heights will also be reported. Inter-rater reliability between parent-measured height using the smartphone app and Health Visitor measured height using a stadiometer will be assessed using Gwet's Agreement Coefficient.¹⁹

Aim 2

All children will undergo a developmental assessment in the community, conducted by a health visitor with input from the child's parent, as part of standard care (ASQ-3 questionnaire). A subset of 150 children will, in addition, have a gold standard developmental assessment conducted by a child psychologist using the GMDS, which measures gross motor, fine motor, social, language, visual-spatial and practical reasoning skills.

Data on socioeconomic circumstances will be used to model the probability of a child's risk of developmental delay or sub-threshold delay on the ASQ-3 (n=600) and GMDS (n=150). Poor growth (assessed by the algorithm) will then be included in these models to assess whether model fit is improved, and whether poor growth contributes to the predictive power of socioeconomic variables to predict developmental delay.

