Concurrent validity of the ASQ-3 and GMDS will be assessed. Each measure will be used to assess whether the participant has any degree of developmental delay, based on measure-dependent cut offs. The degree of agreement will be assessed using Cohen's kappa, and interpreted using existing guidelines, where a kappa value of >0.4 reflects moderate agreement, and a kappa of >0.6 reflects substantial agreement.²⁰ The GMDS will also be used as a gold standard child development measure to assess the performance of the ASQ-3. Sensitivity and specificity will be calculated to assess the ability of the ASQ-3 of identifying children identified as having a delay by the GMDS.

The outcomes for Aim 2 are the correlation between the ASQ-3 and the GMDS; and the change in sensitivity with the addition of anthropometric and developmental data to an existing vulnerability index.

Qualitative analyses

To further our understanding of the acceptability of the proposed screening programme, we will conduct two focus groups with parents participating in the study, as well as one focus group with health visitors. The transcribed data from the focus groups with caregivers and health visitors will be used to generate coding categories and will be analysed using NVivo, using thematic analysis.

11. Ethics

Research Ethics Committee approval will be sought. This is not a trial and there is no intervention which could result in direct harm to participants. However, there are potential indirect harms related to the study. We will aim to mitigate these as far as possible and will include detail of these potential harms in the patient information and informed consent procedures.

Firstly, the study will involve collecting sensitive data, which if handled incorrectly could lead to identification of individual children or groups of children. The study procedures to de-identify or pseudo-anonymise children will reduce the risk of identification of individuals. The potential for 'group harm', in which a particular subpopulation (e.g. by area, ethnicity or gender) are stigmatized because of study findings, such as the finding of high prevalence of growth failure, will be minimized in publications and dissemination of study findings, by not releasing results relating to small areas.

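### ASQ-3 accuracy against the GMDS rests on a voluntary subsample whose size and timing the protocol states inconsistently, and masking of the psychologist is not specified

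*Protocol*

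**What the plan says.** Under Aim 2, section 10.2 states: "Sensitivity and specificity will be calculated to assess the ability of the ASQ-3 of identifying children identified as having a delay by the GMDS". The same paragraph plans Cohen's kappa for agreement on any delay. The ASQ-3 is standard care for every child (n=600 in the section 10.2 models), while the GMDS is done in a subset.

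The protocol describes that subset in two ways.

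- **Later invitation.** The synopsis (section 4, Aim 2) says: "Following the 2.0-2.5 year contact, a random sample of 150 children will also be invited to enrol in a sub-study". Section 9.3, Development sub-study, says: "A randomly selected subset of 150 children will also be invited to an additional appointment with a child psychologist". It adds that this is outside standard care, uses its own consent form (Form 5), and concerns children who will be 3 to 4 years old.
- **Baseline assessment.** Section 9 says of the health visitor lists: "From these lists, children will be randomly selected, with replacement, in two groups", of 480 and 150, and that "group 2 will additionally have a gold standard child development assessment conducted at baseline". Section 9.4 (schedule of study interventions) says: "These children will undergo a neurodevelopmental assessment during their routine health visitor visit".

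The number 150 also shifts. It is the number invited in the synopsis, in section 9.3 and in the sub-study text of section 9.4. It is the number assessed in section 9.8 and in section 10.2: "A subset of 150 children will, in addition, have a gold standard developmental assessment conducted by a child psychologist using the GMDS".

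Section 8 has parents complete the ASQ-3 before the baseline visit. No section says whether the psychologist sees the ASQ-3 or the growth result.

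**The concern.** Random selection protects the invitation, not the acceptance. By the time of the baseline visit the parents have answered the ASQ-3 themselves. The health visitor, who also handles the ASQ-3, administers Form 5. Section 5.3 presents the GMDS as something that could support an educational care plan, which may attract worried families. The protocol also mentions distress and stigma (section 11) and the chance that results are used to a child's disadvantage (section 5.3), which may deter the same families. If uptake differs by ASQ-3 result, accuracy computed only in children with both tests carries partial verification bias.

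A psychologist who knows the ASQ-3 result may also score towards it. An analysis plan cannot undo that afterwards.

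The timing matters in its own right. Section 10.2 calls the comparison concurrent validity. A baseline ASQ-3 at 2.0 to 2.5 years set against a GMDS at 3 to 4 years would be 0.5 years (3.0 − 2.5) to 2 years (4.0 − 2.0) apart.

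The synopsis says these data will inform a larger application on ASQ-3 sensitivity, so a shifted estimate would carry forward.

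**Working it through.** **No figure to reproduce.** The protocol gives no expected accuracy, uptake or derivation for the 150. Its only power statement (section 10.1) concerns Aim 1. What follows shows scale under stated assumptions.

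**1. Selective uptake.** Let Se and Sp be the true values, and let R be uptake in ASQ-3-positive children divided by uptake in ASQ-3-negative children. Then:

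- apparent Se = Se·R / (Se·R + 1 − Se)
- apparent Sp = Sp / (Sp + (1 − Sp)·R)

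Assumed: Se 0.70, Sp 0.85 (not in the protocol).

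| R | Apparent Se | Apparent Sp |
|---|---|---|
| 0.5 | 0.35/(0.35+0.30) = 0.538 | 0.85/(0.85+0.075) = 0.919 |
| 0.75 | 0.525/(0.525+0.30) = 0.636 | 0.85/(0.85+0.1125) = 0.883 |
| 1 | 0.700 | 0.850 |
| 1.25 | 0.875/(0.875+0.30) = 0.745 | 0.85/(0.85+0.1875) = 0.819 |
| 2.0 | 1.40/(1.40+0.30) = 0.824 | 0.85/(0.85+0.30) = 0.739 |

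Equal uptake gives no bias. Otherwise the two figures move in opposite directions, and which one rises depends on R.

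**2. Review bias.** Assume 10% delay. The cell proportions are TP 0.070, FN 0.030, FP 0.135, TN 0.765. If knowledge of the ASQ-3 moves 10% of discordant children to agreement:

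- Se = (0.070 + 0.0135) / (0.0835 + 0.027) = 0.756
- Sp = (0.765 + 0.003) / (0.768 + 0.1215) = 0.863

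Moving 5% gives 0.729/0.857 and moving 20% gives 0.802/0.877. Both figures rise each time.

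**3. Does weighting recover the truth?** Take 1,000 children with the cells above and uptake of 0.90 (ASQ-3 positive) and 0.45 (negative), so R = 2.

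- Children with a GMDS: TP 63, FN 13.5, FP 121.5, TN 344.25.
- Unweighted: 63/76.5 = 0.824 and 344.25/465.75 = 0.739.
- Weighting positives by 1/0.90 and negatives by 1/0.45 restores 70, 30, 135 and 765, that is 0.70 and 0.85.

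The weights need only the ASQ-3 results of all children, which are already collected. Recovery holds if uptake depends on the ASQ-3 result alone.

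**4. Precision, for comparison.** With 150 assessed and assumed delay of 5%, 10% or 20%, there are about 8, 15 or 30 delayed children. Exact 95% intervals for sensitivity are about 0.35–0.97 (6/8), 0.38–0.88 (10/15) and 0.51–0.85 (21/30). If 150 is instead the number invited and 60% accept (assumed), 150 × 0.60 = 90 are assessed, with about 9 delayed at 10%.

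**The case against.** Several stronger readings are tempting, and the protocol does not support them.

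- **That the reference test is unblinded.** The text is silent on masking. Silence supports only that masking is not specified.
- **That the ASQ-3 result decides who gets the GMDS.** Selection is described as random throughout, so there is no verification by test result by design.
- **That invitation always follows the ASQ-3 contact.** That is one version. Under the list-based version families are chosen beforehand, and section 9.2 sends study information out with the ASQ-3. The case for selective uptake is then weaker, though it does not vanish: the GMDS still needs consent, and section 8 has parents complete the ASQ-3 before the visit.
- **That sensitivity will be too high and specificity too low.** This needs higher uptake in ASQ-3-positive families. Lower uptake reverses it, and review bias pushes specificity the other way.

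The two mechanisms also lean on different versions of the sub-study. A GMDS within the routine visit leaves no extra appointment to decline, and a separate appointment weakens the worry about a shared visit.

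It is also fair to say that a weighted estimator may be left to a SAP, that this is a secondary objective of a pilot, and that the intervals are at least as wide as plausible bias. These points limit the weight of the finding. They do not remove it: a confidence interval does not display bias, and masking, timing and the meaning of 150 are matters of conduct that the protocol itself must settle. Sections 9.8 and 10.2 do read 150 as assessed, but three other places read it as invited. If sampling with replacement in section 9 means replacing decliners, that would secure the number without removing the selection.

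**Conclusion.** The point holds as a moderate one. Two contradictions stand on the text: 150 invited against 150 assessed, and a baseline GMDS against a later appointment at age 3 to 4. Masking of the psychologist is unspecified. Selective uptake and review bias therefore cannot be excluded, but neither is demonstrated.

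With assumed true values of 0.70 and 0.85, an uptake ratio between 0.5 and 2.0 puts apparent sensitivity anywhere from 0.54 to 0.82 and specificity from 0.92 to 0.74. A ratio of 1 gives no bias. Review bias of 5% to 20% of discordant children, at 10% prevalence, would raise sensitivity to 0.73–0.80 and specificity to 0.86–0.88. All accuracy, uptake and prevalence values are assumptions, because the protocol gives none.

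**What to change.** 1. Reconcile the synopsis and section 9.3 with sections 9 and 9.4 on when the 150 are selected and when the GMDS is done.
2. State that 150 is the number assessed. If it is the number invited, give the expected number with a GMDS and correct sections 9.8 and 10.2.
3. Add one sentence saying that the psychologist scores the GMDS without sight of the ASQ-3 or growth result.
4. Compare the ASQ-3 results of children with and without a GMDS. As a sensitivity analysis, report sensitivity, specificity and kappa weighted by ASQ-3 result (Begg-Greenes or inverse probability) beside the unweighted figures. The detail can sit in the SAP.

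The cost is a few lines of text and a short analysis on data already collected. The weighting assumes that uptake depends only on the recorded ASQ-3 result, so it does not correct for parental concern beyond that score. It also slightly widens intervals that are already wide.

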6.2. Secondary objective

Generate pilot data to investigate the best indicators to detect poor school readiness and/or developmental problems in early childhood.

Within the secondary objective we aim to test the following two hypotheses:

- 1. The addition of growth and development data to other environmental and socioeconomic variables (including Index of Multiple Deprivation) increases the pick-up rate of children at risk of poor school readiness and/or children with delayed development.
- 2. There is strong correlation between the existing measurement of child development in pre-school age children (ASQ-3) and a gold standard developmental assessment by a child psychologist.

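### Aim 2 names a strong correlation of ASQ-3 with GMDS as its hypothesis and outcome, but the specified analysis is Cohen's kappa, sensitivity and specificity on a yes/no delay split, which does not address it

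*Protocol*

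**What the plan says.** The target is called a correlation wherever it is stated as an aim or an outcome:

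- Protocol, Section 4 (synopsis): the sub-study of 150 children is to "investigate the correlation between the ASQ-3 and development assessed by a child psychologist" using the GMDS. The same section lists a strong correlation as Aim 2 hypothesis 2.
- Protocol, Section 6.2, hypothesis 2: "There is strong correlation between the existing measurement of child development in pre-school age children (ASQ-3) and a gold standard developmental assessment". No value is given for 'strong'.
- Protocol, Section 10.2, Aim 2: "The outcomes for Aim 2 are the correlation between the ASQ-3 and the GMDS", plus the change in sensitivity when anthropometric and developmental data are added to a vulnerability index.

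The method for comparing the two instruments is also in Section 10.2. First the scores are dichotomised: "Each measure will be used to assess whether the participant has any degree of developmental delay, based on measure-dependent cut offs". Then "The degree of agreement will be assessed using Cohen's kappa", read against the guideline that "a kappa value of >0.4 reflects moderate agreement, and a kappa of >0.6 reflects substantial agreement". Finally, "Sensitivity and specificity will be calculated to assess the ability of the ASQ-3" against delay on the GMDS. No correlation coefficient is named, and no analysis sets ASQ-3 scores against GMDS scores.

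**The concern.** The Protocol does not leave the method open. It fixes the scale (delay yes or no), the statistic (kappa) and the bands for reading it, and these belong to a different question from the one in the hypothesis. Correlation of scores asks whether children who score lower on one instrument also score lower on the other, across the whole range. Kappa on a dichotomy asks whether the two cut-offs classify the same children as delayed, beyond chance. An analysis that follows the method text would not produce the outcome named in the same section.

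The risk is one of interpretation. If kappa is the only summary for hypothesis 2, it is likely to be read as the answer to it. As shown below, scores that correlate well can give a kappa that the Protocol's bands label only moderate. The synopsis says the sub-study data will inform a larger grant application on the ASQ-3, so a misreading would carry forward.

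**Working it through.** The Protocol gives no power, precision or expected-value figure for the ASQ-3 and GMDS comparison, so there is none to reproduce. The check asks what kappa a given score correlation implies, and how precisely each is estimated.

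**Inputs from the Protocol (Section 10.2).** 150 children with both measures; kappa bands at 0.4 and 0.6.

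**Assumptions, since the Protocol gives no figures.** Scores are bivariate normal with correlation ρ. Delay rates are p_A on the ASQ-3 and p_B on the GMDS; the main case is equal rates of 10% and 20%.

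**Formulas.** Let p11 be the probability that both measures show delay, from the bivariate normal distribution function at the two cut-offs.

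- Observed agreement: po = p11 + (1 − p_A − p_B + p11)
- Chance agreement: pe = p_A·p_B + (1 − p_A)(1 − p_B)
- Kappa = (po − pe)/(1 − pe)

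**Worked case, ρ = 0.7, 10% delay on both.** p11 = 0.0468. po = 0.0468 + (0.80 + 0.0468) = 0.8936. pe = 0.01 + 0.81 = 0.82. Kappa = (0.8936 − 0.82)/0.18 = 0.41.

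**Results.**

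| Score correlation | Delay 10% / 10% | Delay 20% / 20% | ASQ-3 20%, GMDS 10% |
|---|---|---|---|
| 0.7 | 0.41 | 0.46 | 0.38 |
| 0.8 | 0.51 | 0.56 | 0.46 |

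Over equal rates from 5% to 50%, kappa runs from 0.36 to 0.49 at ρ = 0.7 and from 0.47 to 0.59 at ρ = 0.8. The same correlation thus maps to different kappas depending on where the cut-offs fall, and at ρ = 0.8 none of these values reaches 0.6.

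**Precision with 150 children, both at ρ = 0.7.**

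- Correlation, by Fisher's z: atanh(0.7) = 0.867; half-width 1.96/√147 = 0.162; back-transforming 0.867 ± 0.162 gives a 95% confidence interval of 0.61 to 0.77.
- Kappa, by simulating samples of 150: the central 95% of observed values is about 0.15 to 0.63 at 10% delay and 0.27 to 0.62 at 20% delay.

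The kappa ranges run from below the moderate line to above the substantial line, so at this sample size the band reported would depend heavily on chance.

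**The case against.** Several points on the other side are sound.

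- *The outcome itself promises a correlation, and the coefficient could be fixed in a statistical analysis plan.* The choice between Pearson and Spearman could indeed be left to such a plan. But the Protocol has already written out the method for this comparison, on a dichotomy. That is a stated method which misses the question, and not merely detail left for later.
- *Kappa is a different quantity from r, so a lower kappa is not a biased r.* This stands. A reader might infer from the table that kappa understates the correlation. The documents do not support that reading: the two have different definitions and benchmarks. With equal delay rates kappa equals the phi coefficient, which is itself a correlation of the two classifications, though not of the scores. The table shows only that kappa cannot stand in for strength of score correlation.
- *No decision rule is attached to the bands.* This also stands. A reader might infer that hypothesis 2 would be rejected if kappa fell below 0.6. The Protocol uses the bands as descriptive labels, ties neither to the hypothesis, and gives no threshold for 'strong', so a rate of false rejection cannot be claimed.
- *Classification is the practical purpose.* Section 4 and the development sub-study text in Section 9.4 speak of the sensitivity of the ASQ-3, and a high correlation can coexist with disagreement at the cut-offs. This is a good reason to keep kappa, sensitivity and specificity at full standing. A reader might conclude that they should become secondary to a correlation; the stated purpose argues against that.
- *'Correlation' may have been meant loosely.* Possibly. In that case the hypothesis and outcome need rewording, and the mismatch remains until they are.

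**Conclusion.** The mismatch holds on the text alone and needs no assumptions: the hypothesis and the outcome are a correlation, and the specified analyses are agreement and accuracy on a yes/no split. The size of the gap between the two quantities rests on assumed bivariate normal scores and assumed delay rates. In the main case of 10-20% delay on both measures, correlations of 0.7 and 0.8 correspond to kappa of about 0.41-0.46 and 0.51-0.56, all within the moderate band. Unequal rates, which separate cut-offs for each measure make possible, lower these figures further in the case tried. This concerns a secondary objective of a feasibility pilot and does not touch the primary endpoint. It is nevertheless worth correcting, because a named outcome has no matching analysis and the remedy is small.

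**What to change.** In Section 10.2, Aim 2, do one of the following.

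1. Add a Pearson or Spearman correlation of the ASQ-3 and GMDS scores, with a 95% confidence interval, as the analysis of hypothesis 2. State which scores are used and what value counts as strong. Keep Cohen's kappa, sensitivity and specificity, undemoted, as the analyses of agreement and accuracy at the cut-offs.
2. If agreement on delay is what is meant, restate hypothesis 2 (Sections 4 and 6.2) and the Aim 2 outcome (Section 10.2) as agreement on delay classification.

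The first option costs a few lines of text and one further analysis. It needs no extra visits or assessments, provided the scores behind the cut-offs are recorded as well as the delay classification. The second costs only wording.
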